13.2 Publication policy and confidentiality

The clinical investigation will be registered in a publicly accessible database prior to the enrolment of the first patient.

 PERFECT LENS PL-RIS01	Clinical Investigation Plan	Page no.	47 z 55
		Version	02
		Date	2023-07-18

14 Adverse events, adverse device effects and device deficiencies

During the course of the planned clinical investigation, utmost attention will be given to detecting any potential adverse events or unfavourable discoveries. Should any adverse event take place, the safety of the subject will be the primary concern, and suitable medical intervention will be provided promptly. All adverse events, regardless of severity and whether they are attributed to the investigational device or clinical investigation-related procedure, will be diligently recorded in the relevant sections of the subject's worksheets (CRFs).

All findings related to adverse events must be documented in the "Adverse Event (AE)" section of the subject's worksheets (CRFs). These events are categorized as either serious or non-serious, as well as related or unrelated to the investigational device/procedure. The method of reporting or documenting these adverse events varies depending on their category (serious or non-serious).

If the device operator, a bystander, or any third person experiences a severe adverse event possibly linked to the investigational device, it must be reported using an AE form along with a Device Deficiency form if applicable.

14.1 Definitions

The following are the definitions as per ISO 14155:2020

14.1.1 Adverse Event (AE)

Any untoward medical occurrence, unintended disease or injury, or untoward clinical signs (including abnormal laboratory findings) in subjects, users or other persons, whether or not related to the investigational medical device and whether anticipated or unanticipated. This definition includes events related to the investigational medical device. This definition includes events related to the procedures involved. For users or other persons, this definition is restricted to events related to investigational medical devices.

14.1.2 Adverse Device Effect (ADE)

Adverse event related to the use of an investigational medical device or to the procedure. This definition includes adverse events resulting from insufficient or inadequate instructions for use, deployment, implantation, installation, or operation, or any malfunction of the investigational medical device. This definition includes any event resulting from use error or from intentional misuse of the investigational medical device.

14.1.3 Device Deficiency (DD)

An inadequacy of a medical device with respect to its identity, quality, durability, reliability, safety usability, safety or performance. Device deficiencies include includes malfunctions, use errors, and inadequacy in the information supplied by the manufacturer including labelling. This definition includes device deficiencies related to the investigational medical device. DD can become (might lead to) serious adverse events (SAE) if:

- a) suitable action had not been taken, or
- b) intervention had not been made, or
- c) if circumstances had been less fortunate

 PERFECT LENS PL-RIS01	Clinical Investigation Plan	Page no.	48 z 55
		Version	02
		Date	2023-07-18

These DDs are handled using the SAE reporting system.

14.1.4 Serious Adverse Event (SAE)

According to MDR 2017/745, serious adverse event means any adverse event that led to any of

the following:

- a) death,
- b) serious deterioration in the health of the subject, that resulted in any of the following:
 - a. life-threatening illness or injury,
 - b. permanent impairment of a body structure or a body function,
 - c. hospitalization or prolongation of patient hospitalization,
 - d. medical or surgical intervention to prevent life-threatening illness or injury or
 - e. permanent impairment to a body structure or a body function,
 - f. chronic disease,
- c) fetal distress, fetal death or a congenital physical or mental impairment or birth defect;

According to the ISO 14155:2020: planned hospitalization for a pre-existing condition, or a procedure required by the CIP, without serious deterioration in health, is not considered a serious adverse event.

Any adverse events that do not satisfy these descriptions are defined as being non-serious.

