14.1.5 Serious Adverse Device Effects (SADE)

Adverse device effect (ADE) that has resulted in any of the consequences characteristic of a serious adverse event.

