14.1.6 Anticipated and Unanticipated Serious Adverse Device Effects (ASADE and USADE)

Anticipated serious adverse device effect (ASADE) is a Serious Adverse Device Effect (SADE) which by its nature, incidence, severity or outcome has been identified in the study protocol. An Unanticipated serious adverse device effects (USADE) is a Serious Adverse Device Effect (SADE) which by its nature, incidence, severity or outcome has not been identified in the study protocol.

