14.5 Expedited Reporting of Adverse Events

An AE should be classified as SERIOUS if it:

- (a) Caused or led to death.
- (b) Was life threatening (i.e., the AE placed the subject at immediate risk of death).
- (c) Required or prolonged inpatient hospitalization (i.e., the AE required at least a 24-hour inpatient hospitalization or prolonged a hospitalization beyond the expected length of stay).
- (d) Was sight threatening.
- (e) Was disabling (i.e., the AE resulted in a substantial disruption of the subject's ability to carry out normal life functions).
- (f) Resulted in a congenital anomaly/birth defect (i.e., an adverse outcome in a child or fetus of a subject due to participation in this study).
- (g) Does not meet any of the above serious criteria but jeopardized the subject by requiring medical or surgical intervention to prevent one of the outcomes listed above.

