14.6 Anticipated adverse events

All ocular AEs in the study eye must be reported on the relevant CRF. AEs will be categorized by degree of harm to the subject (mild, moderate, or severe).

Ocular conditions or diseases present at the time of study enrolment will be considered as "baseline." Changes in a chronic condition or disease that are consistent with natural disease progression are not considered SRAEs.

AEs that might occur include, but are not limited to, the following:

- (a) Corneal abrasion
- (b) Anterior chamber cell and flare requiring initiation of steroid Treatment.
- (c) Corneal edema
- (d) Cystoid Macular Edema
- (e) Retinal issues

 PERFECT LENS <hr/> PL-RIS01	Clinical Investigation Plan	Page no.	51 z 55
		Version	02
		Date	2023-07-18

(f) Elevated IOP requiring Treatment

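### Sections 14.1.4 and 14.5 of the protocol give opposite seriousness status to an adverse event that meets 14.5(d), (e) or part of (g) but no item of 14.1.4

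*Protocol*

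**What the plan says.** Section 14.1.4 defines a serious adverse event by a list attributed to the MDR. The list covers death; serious deterioration in health with one of several named results; and fetal or congenital harm. The named results are life-threatening illness or injury, permanent impairment, hospitalization or its prolongation, intervention to prevent life-threatening harm or permanent impairment, and chronic disease. The section then closes the list: "Any adverse events that do not satisfy these descriptions are defined as being non-serious".

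Section 14.5, headed as expedited reporting, states a second rule: "An AE should be classified as SERIOUS if it" meets any of seven criteria, (a) to (g). Criterion (d) is "Was sight threatening". Criterion (e) is disabling, explained as a substantial disruption of normal life functions. Criterion (g) takes in events that meet none of the others but put the subject in jeopardy by "requiring medical or surgical intervention to prevent one of the outcomes listed above".

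Other sections depend on the term. Section 14.1.5 defines a SADE as an "Adverse device effect (ADE) that has resulted in any of the consequences characteristic of a serious adverse event", and 14.1.6 builds the anticipated and unanticipated classes on the SADE. The introduction to section 14 says that the way an event is reported or documented depends on whether it is serious. Section 14.7 gives the investigator 2 business days to report ADEs and SAEs to the sponsor, and 7 business days for adverse events generally.

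**The concern.** Two lists of seriousness criteria in one protocol are not a fault in themselves: the second could add study-specific items to the first. Here the closing sentence of 14.1.4 blocks that reading, because it assigns every event outside its own list to the non-serious class. Any event reached only by 14.5 then has two contradictory classifications.

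The additions in 14.5 include an ocular criterion, and this is a laser treatment of the eye. Safety is part of the stated objective (section 6.2.4), and section 6.2.1 names injury from laser energy as the principal risk. Two people who each apply the protocol faithfully could classify the same ocular event in opposite ways. The SAE listing and count would then depend on which section they happened to use.

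**Working it through.** The check is a comparison of the two lists; the only arithmetic is on the reporting limits. Items d and e under serious deterioration in 14.1.4 are read together as one item (intervention to prevent life-threatening harm or permanent impairment), since the split looks like an effect of layout.

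| 14.5 criterion | Counterpart in 14.1.4 |
|---|---|
| (a) death | yes, death |
| (b) life threatening | yes, life-threatening illness or injury |
| (c) hospitalization | yes, hospitalization |
| (d) sight threatening | none; impairment must be permanent |
| (e) disabling | none; impairment must be permanent |
| (f) congenital harm | yes, fetal or congenital harm |
| (g) intervention to prevent a listed outcome | partial; covers only prevention of life-threatening harm or permanent impairment |

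Four criteria, (a), (b), (c) and (f), have counterparts. Two, (d) and (e), have none. Criterion (g) goes beyond 14.1.4 where the outcome averted is (d), (e) or hospitalization (c), because 14.1.4 does not count intervention to prevent any of these as such.

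**Is the conflicting set empty?** No. Criteria (d) and (e) require neither permanence, hospitalization nor intervention. Take an event judged sight threatening that resolves untreated and leaves no lasting loss. It meets 14.5(d), so it is serious. It meets no item of 14.1.4, so by that section's last sentence it is non-serious. A temporarily disabling event gives the same result through (e), and an intervention that averts a hospital stay can give it through (g).

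**Do the differences in the other direction conflict?** No. Permanent impairment and chronic disease are named only in 14.1.4, and 14.5(c) adds a 24-hour minimum stay. But 14.5 has no sentence that makes everything else non-serious, so an event that only 14.1.4 reaches is serious without contradiction.

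**Is there a precedence rule?** Neither section refers to the other, and nothing elsewhere in the available text ranks them.

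**Consequence for the reporting limit (14.7).**
- Event that is not an ADE: 2 business days if serious, 7 if not; difference 7 − 2 = 5 business days.
- Event that is an ADE: 2 business days either way; difference 2 − 2 = 0.

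**Consequence for SADE status (14.1.5).** It arises only for device- or procedure-related events, so the SADE effect and the 5-day difference do not fall on the same event.

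**The case against.** The strongest reply is that 14.1.4 reproduces a regulatory definition, while 14.5 supplements it with criteria suited to an eye study, so a sensible investigator would treat an event meeting either list as serious. That may well happen in practice. As a reading of the text, however, it requires ignoring the last sentence of 14.1.4. The heading of 14.5 does not confine it to reporting either: its operative instruction is to classify, and the investigator's deadlines are in 14.7.

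The second reply is that the set is small. This stands. A sight-threatening event will often lead to permanent impairment or to intervention to prevent it, and is then serious under both sections. The protocol gives no frequency for the remainder.

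Three stronger readings are tempting, and the protocol does not support them.

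- A reader might infer that the unanticipated class is shown to be affected, since "An Unanticipated serious adverse device effects (USADE) is a Serious Adverse Device Effect (SADE" that the protocol has not identified. But the natural example is a retinal event, and section 14.6 lists "e) Retinal issues" among the events that might occur. Such an event is arguably anticipated by its nature, so the example shows an effect on SADE status, not on USADE status.
- A reader might attach a rate: one such event among the up to 12 patients of section 7.1 would give 1/12 = 8.3% instead of 0/12 = 0%. That is one hypothetical event. Section 8.2 is purely descriptive, and the protocol sets no SAE threshold or safety test that the figure could affect.
- A reader might infer that external reporting is affected. Section 13 has the sponsor inform the ethics committee and competent authority of serious side effects or adverse events. The effect follows only if serious there also qualifies adverse events, which the sentence leaves open.

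The reporting-time effect also depends on what counts as an ADE. If events rated possible under 14.2 count as related, which that section does not say outright, the 5-day difference is limited to events judged unrelated.

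**Conclusion.** The contradiction is real and follows from the wording alone. Two of the seven criteria in 14.5, and part of a third, classify as serious some events that 14.1.4 defines as non-serious, and nothing says which section governs.

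Its reach is limited. It concerns only events that meet (d), (e) or the excess part of (g) and no item of 14.1.4, and how often these would occur is unknown. It affects SAE classification and tallies, SADE status of related events, the documentation route and, for events that are not ADEs, a 5-business-day difference in the limit for reporting to the sponsor. Every such event is still recorded as an adverse event. The three co-primary visual acuity endpoints and the descriptive analysis of efficacy are untouched.

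The conclusion assumes that the split item in 14.1.4 is read as one and that no document outside the available text sets precedence. It deserves correction because the events concerned include ocular harms in a trial whose objective includes safety.

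**What to change.** Reconcile 14.1.4 and 14.5 into one operative definition of seriousness, and have 14.1.5, 14.1.6 and 14.7 refer to it. Which criteria it contains is for the sponsor to decide. One wording that keeps everything already written is to limit the closing sentence of 14.1.4 to events that meet neither list, with the study-specific criteria shown separately from the list attributed to the MDR. If the eCRF, which is not shown, records seriousness, it should follow the same definition.

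The cost is a wording amendment, which under section 10 needs notification to and approval by the ethics committee and the regulatory authorities. If both lists are kept, slightly more events may be counted and handled as serious. No visit, measurement or efficacy analysis changes.

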14.1.5 Serious Adverse Device Effects (SADE)

Adverse device effect (ADE) that has resulted in any of the consequences characteristic of a serious adverse event.

14.1.6 Anticipated and Unanticipated Serious Adverse Device Effects (ASADE and USADE)

Anticipated serious adverse device effect (ASADE) is a Serious Adverse Device Effect (SADE) which by its nature, incidence, severity or outcome has been identified in the study protocol. An Unanticipated serious adverse device effects (USADE) is a Serious Adverse Device Effect (SADE) which by its nature, incidence, severity or outcome has not been identified in the study protocol.

14.2 Adverse event causality

In this study, the investigator is required to assess the causality of each adverse event (AE) based on the degree of responsibility of the investigational device itself or the procedure for implementing a medical device. The assessment should determine whether the AE is related or not related to the medical device, comparator, or study procedure, using the following categories:

- When the event shows no temporal relationship with the use of the investigational device or the procedures related to the application of the investigational device.

 PERFECT LENS PL-RIS01	Clinical Investigation Plan	Page no.	49 z 55
		Version	02
		Date	2023-07-18

- When the serious adverse event does not follow a known response pattern to the medical device (if such response pattern is previously known) and is biologically implausible.
- When the discontinuation of medical device application or the reduction of the level of activation/exposure (if clinically feasible), followed by reintroduction of its use (or an increase in the level of activation/exposure), does not impact the occurrence of the serious adverse event.
- When the event affects a body-site or an organ that cannot be influenced by the device or procedure.
- When the serious adverse event can be attributed to another cause, such as an underlying or concurrent illness/clinical condition, an effect of another device, drug, Treatment, or other risk factors.
- When the event is not influenced by a false result given by the investigational device used for diagnosis, if applicable.

In order to establish the non-relatedness, not all the criteria listed above might be met at the same time, depending on the type of device/procedures and the serious adverse event.

- **Possible:** There is a weak relationship with the use of the investigational device or comparator, but complete exclusion cannot be confirmed. Other potential causes, such as underlying or concurrent illnesses/clinical conditions, or effects of other devices, drugs, or treatments, are also plausible. Cases where relatedness cannot be assessed or when insufficient information is available should also be classified as possible.
- **Probable:** The relationship with the use of the investigational device or comparator appears relevant, and there is no reasonable explanation based on other causes. However, additional information may be required to further ascertain the connection.
- **Causal Relationship:** The event is undeniably associated with the investigational device or comparator or with procedures, leaving no room for doubt regarding the link between the event and the intervention

14.3 Adverse events severity

AEs will be graded on a 3-point scale (mild, moderate, severe) using the following definitions:

- (a) Mild: Discomfort noticed, but there is no disruption of normal daily activity
- (b) Moderate: Discomfort is sufficient to reduce or affect normal daily activity
- (c) Severe: Subject is incapacitated as evidenced by the inability to work or perform normal daily activity

14.4 Follow-up of Adverse Events

AEs will be followed until resolution or stabilization of the event.

The outcome of each AE will be categorized into one of the following groups for reporting

 PERFECT LENS PL-RIS01	Clinical Investigation Plan	Page no.	50 z 55
		Version	02
		Date	2023-07-18

purposes:

- Recovered/resolved
- Recovered/resolved with sequelae (specify type of sequelae)
- Ongoing
- Death

If there is more than one AE, only the AE leading to death will be attributed with a "fatal" outcome.

14.5 Expedited Reporting of Adverse Events

An AE should be classified as SERIOUS if it:

- (a) Caused or led to death.
- (b) Was life threatening (i.e., the AE placed the subject at immediate risk of death).
- (c) Required or prolonged inpatient hospitalization (i.e., the AE required at least a 24-hour inpatient hospitalization or prolonged a hospitalization beyond the expected length of stay).
- (d) Was sight threatening.
- (e) Was disabling (i.e., the AE resulted in a substantial disruption of the subject's ability to carry out normal life functions).
- (f) Resulted in a congenital anomaly/birth defect (i.e., an adverse outcome in a child or fetus of a subject due to participation in this study).
- (g) Does not meet any of the above serious criteria but jeopardized the subject by requiring medical or surgical intervention to prevent one of the outcomes listed above.

14.6 Anticipated adverse events

All ocular AEs in the study eye must be reported on the relevant CRF. AEs will be categorized by degree of harm to the subject (mild, moderate, or severe).

Ocular conditions or diseases present at the time of study enrolment will be considered as "baseline." Changes in a chronic condition or disease that are consistent with natural disease progression are not considered SRAEs.

AEs that might occur include, but are not limited to, the following:

- (a) Corneal abrasion
- (b) Anterior chamber cell and flare requiring initiation of steroid Treatment.
- (c) Corneal edema
- (d) Cystoid Macular Edema
- (e) Retinal issues

 PERFECT LENS <hr/> PL-RIS01	Clinical Investigation Plan	Page no.	51 z 55
		Version	02
		Date	2023-07-18

(f) Elevated IOP requiring Treatment

14.7 Timeline for reporting AE

All adverse events must be reported within 7 business days from the moment the investigators become aware of them. The reporting process involves electronically completing the designated page in the eCRF system.

For Adverse Device Effects (ADE) and Serious Adverse Events (SAE), the Investigator is required to report to the Sponsor within 2 business days of becoming aware of the event using the eCRF. This applies also to the events anticipated or anticipated events.

In case the eCRF is not functioning the investigator is obliged to use any means of communication and notify him within the defined timelines.

15 Vulnerable and dependent population

This investigation strictly prohibits the inclusion of any vulnerable population. Furthermore, individuals who may be dependent on the sponsor or investigator will also be excluded from participating in this clinical investigation.

16 Suspension or premature termination of the clinical investigation

The Sponsor retains the right to terminate or interrupt this investigation at any time, with the following reasons considered:

- Identification of device deficiencies indicating technical problems with the medical device that require attention.
- Incidence or severity of adverse events observed in this or other investigations, suggesting potential health risks to subjects.
- Unsatisfactory subject enrolment.

According to the Medical Device Regulation (MDR), specifically article 77, the Sponsor assumes responsibility for notifying all recruited investigators, Ethics Committees, and, in accordance with local regulations, Competent Authorities regarding the termination of the investigation. The Sponsor must inform Competent Authorities within 15 days, providing a justification. In the event of suspension or premature termination of the investigation due to safety concerns, the Sponsor is obliged to inform all Competent Authorities within 24 hours.

Furthermore, the Sponsor or its representatives reserve the right to discontinue participation at any individual investigational site. Reasons for discontinuation may include:

- Unsatisfactory subject enrolment.
- Inaccurate or incomplete data recording.

 PERFECT LENS	Clinical Investigation Plan	Page no.	52 z 55
PL-RIS01		Version	02
		Date	2023-07-18

- Non-compliance by the investigator or Ethics Committee with current ICH Good Clinical Practice requirements or other applicable regulatory obligations.

